## 1 PROTOCOL REVISION HISTORY

Protocol Revision Number	Protocol Revision Date	Change details
3.0	15 JAN 2021	Initial release
4.0	15 Feb 2021	Response to FDA
5.0	18 Feb 2021	Response to FDA – addition of risk mitigation strategy for trial
6.0	19 FEB 2021	Response to FDA - Addition of Investigator Agreement requirements
7.0	22 Feb 2021	Addition of secondary endpoints and inclusion/exclusion criteria clarification
8.0	22 Jun 2021	Correction of typographical errors Page 18 - 7.3.3 Intravascular Ultrasound Assessment Addition of clarification regarding safety measures associated with the final IVUS run and blinding of the interventional cardiologist Page 19 –8.2 Correction of Troponin T to Troponin I as per CRFs Page 25 – 11.8 Stopping rules: Addition of stopping rules Page 31 - 12.5 – Medical Monitor: Addition of a Medical Monitor Page 31 –Clinical events committee adjudication is now section 12.6, previously 12.5 Page 37 - Addition of References
9.0	17 Aug 2021	Response to FDA: Page 25 – 11.8 Stopping rules: Clarification on Stopping Rules Page 31 – 12.6 Clinical events committee adjudication: Clarification Page 32 - 13.3 Clinical events committee: Clarification
9.1	17 Aug 2021	Response to CMS office: Page 14 – 6.4.2 SECONDARY ENDPOINTS: Clinical endpoints assessment at 30 AND 270 day follow-up; Addition of CCS Class assessment Page 15 – 7.2 7.2 Schedule of assessments: Addition of CCS class Page 19 - 8.3 30-day & 270 day Follow-ups: addition of angina status and CCS class Page 25 - 11.5 Anticipated Benefits: Clarification Other Changes Correction of typographical errors Page 15 – 6.5 Screening, Enrollment, and Randomization: Clarification of Randomization Page 25 - 11.7 Justification of Trial– Addition of References
9.2	17-Nov-2021	Response to FDA: Page 25 – 11.8 Stopping rules: Clarification on Stopping Rules
10	10-Nov-2022	Update to Investigator Information Page 11 - 6.2 Number of Subjects and Clinical Sites: Update to site enrollment allotment Page 33 - 13.5.2 MONITORING: update to source data verification for 30 and 270 day Follow-up Correction of typographical errors
11	02-Mar-2023	Page 11 - 6.2 Number of Subjects and Clinical Sites: Update to site enrollment allotment

Page | 2

**CONFIDENTIAL AND PROPRIETARY:** This document and the information contained there-in may not be reproduced, used or disclosed without written permission from the Principal Investigators.

Version: 11\_dtd02Mar2023

IDE G210030

## ABBREVIATIONS AND DEFINITIONS OF TERMS

ACS	Acute Coronary Syndrome
CABG	Coronary Artery Bypass Graft
CAD	Coronary Artery Disease
Cath Lab	Cardiac Catheterization Laboratory
CVA	Cerebrovascular accident
DES	Drug-eluting stent
EEM	External Elastic Membrane
DM	Diabetes Mellitus
HIPAA	Health Insurance Portability and Accountability Act
ISMMS	Icahn School of Medicine at Mount Sinai
MACE	Major Adverse Cardiovascular Event
MI	Myocardial Infarction
NSTEMI	Non-ST Elevation MI
PCI	Percutaneous Coronary Intervention
PHI	Protected Health Information
PI	Principal Investigator
RA	Rotational Atherectomy
ST	Stent thrombosis
STEMI	ST Elevation MI
TIMI	Thrombolysis in Myocardial Infarction
TLR	Target lesion revascularization
TVR	Target vessel revascularization
UA	Unstable Angina

## 4 BACKGROUND INFORMATION AND RATIONALE

### 4.1 Introduction

Patients undergoing percutaneous coronary intervention (PCI) for calcified lesions experience a high rate of major adverse cardiovascular events, including in the contemporary drug-eluting stent era.(1-3) Rotational atherectomy (RA) is an established tool in interventional cardiology for treatment of calcified coronary lesions.(4) The primary rationale for use of RA is to modify physical attributes of calcified plaque to facilitate balloon angioplasty and stent deployment. Although RA is recommended for plaque preparation in severely calcified lesions, a large number of patients demonstrate high residual stent diameter stenosis after RA and stent implantation resulting in similar restenosis rates and major adverse cardiac event (MACE) between patients treated with and without RA.(5, 6) Several clinical trials showed no benefits with aggressive strategy for procedural success or target vessel revascularization.(7) The study hypothesis is that calcified lesion preparation with rotational atherectomy followed by cutting balloon angioplasty (ROTA + CUT) will result in increased lumen gain, more optimal stent expansion and decreased MACE compared to rotational atherectomy followed by plain old balloon angioplasty (ROTA + POBA) in patients with calcified lesions.

### 4.2 Study Devices

Model	Manufacturer	Region	Status
ROTAPRO™	Boston Scientific	Global	Commercially Available
Wolverine™ Coronary Cutting Balloon Monorail & Over-the-wire	Boston Scientific	Global	Commercially Available

### 4.3 Compliance Statement

This study will be conducted in full accordance with all applicable Federal and State laws and regulations including 45 CFR 46, and the HIPAA Privacy Rule. Any episode of noncompliance will be documented.

The Principal Investigators will perform the study in accordance with the protocol, and will report any unexpected problems in accordance with applicable IRB Policies and Procedures and all Federal requirements.

Page | 10

**CONFIDENTIAL AND PROPRIETARY:** This document and the information contained there-in may not be reproduced, used or disclosed without written permission from the Principal Investigators.

Version: 11\_dtd02Mar2023

IDE G210030

Effective Date: 3/23/2023

End Date: 2/14/2024

## 5 STUDY OBJECTIVES

The aim of the study is to compare the effect of two lesion modification strategies, ROTA+CBA and ROTA+POBA for the treatment of obstructive calcified lesion on minimum lumen area (MLA), stent expansion and apposition obtained with IVUS, procedural- and short-term clinical outcomes. The primary endpoint will be post-procedural Minimum Stent Area (MSA, mm^2) assessed by IVUS.

The secondary aim of the study is to assess the IVUS and quantitative coronary angiography (QCA) parameters both acute post device and final (post stent and post dilatation) between the ROTA+CBA and ROTA+POBA arms. Further secondary endpoints will include percent stent expansion and stent strut malapposition, procedure related complications, and 1 & 9 - month MACE among the list.

## 6 INVESTIGATIONAL PLAN

### 6.1 Study Design

This is a prospective, multi-center randomized pilot study of 60 patients with stable CAD undergoing PCI for a *de novo* calcified lesion with drug eluting stent implantation. Patients with target vessel reference diameter of  $\geq 2.5$  mm and  $\leq 4.0$  mm, lesion length  $\geq 5$  mm and moderate to severe calcification confirmed by angiography will undergo pre-procedural IVUS assessment, if feasible. Subjects with moderate or severe calcification for at least 5 consecutive mm in a *de novo* lesion, confirmed by angiography, will be enrolled. Enrolled subjects will be randomized in a 1:1 fashion to either ROTA + CUT or ROTA + POBA group. Rotational Atherectomy will be performed using Burr: Artery ratio of 0.4 to 0.6 in both arms. Intra-procedural IVUS pullbacks will be performed after lesion preparation, prior to stent implantation and after stenting. Upon PCI completion, operators will be blinded to final, post angioplasty IVUS results. An unblinded physician will review the results of this final IVUS run for safety signals not present on fluoroscopy. All patients will receive a drug-eluting stent after plaque preparation.

### 6.2 Number of Subjects and Clinical Sites

The pilot study of 60 patients will take place at Mount Sinai Hospital ([name]) and St. Francis Heart Hospital ([name]) with up to 48 patients enrolled at each site. All study subjects will sign an informed consent.

### 6.3 Study Population

Patients  $\geq 18$ -years-old undergoing PCI for a *de novo* calcified lesion with planned drug-eluting stent implantation

Page | 11

**CONFIDENTIAL AND PROPRIETARY:** This document and the information contained there-in may not be reproduced, used or disclosed without written permission from the Principal Investigators.

Version: 11\_dtd02Mar2023

IDE G210030

Effective Date: 3/23/2023

End Date: 2/14/2024

### 6.3.1 Inclusion Criteria

A subject who meets ***all the following criteria*** potentially ***may be included*** in the trial:

- 1) Patient (or legal guardian) is  $\geq 18$  years if age and understands the trial requirements and the treatment procedures and provides written informed consent
- 2) Patient undergoing PCI for a *de novo* calcified lesion with planned rotational atherectomy and planned drug-eluting stent implantation of a lesion with target vessel reference diameter  $\geq 2.5$  mm and  $\leq 4.0$  mm, lesion length  $\geq 5$  mm and moderate to severe calcification by angiography
- 3) Patient is eligible for PCI
- 4) Patient is willing and able to comply with all protocol-required follow-up evaluations

### 6.3.2 Exclusion Criteria

A subject who meets ***any of the following criteria will not be included*** in the trial:

- 1) Patient in cardiogenic shock
- 2) Planned surgery (cardiac and non-cardiac) within 6 months after the index procedure unless the dual-antiplatelet therapy (DAPT) can be maintained throughout the peri-surgical period
- 3) Patient undergoing primary PCI for ST-segment elevation myocardial infarction
- 4) Subject is pregnant, nursing, or is a woman of child-bearing potential who is not surgically sterile,  $< 2$  years postmenopausal, or does not consistently use effective methods of contraception
- 5) Patient has any other serious medical illness (e.g., cancer, end-stage congestive heart failure) that may reduce life expectancy to less than 12 months
- 6) Currently participating in another investigational drug or device study
- 7) Patient referred to coronary artery bypass grafting after heart team discussion

### 6.3.3 Angiographic Specific Exclusion Criteria

- 8) Lesion(s) with angulation  $> 45$  degrees by visual estimate
- 9) Lesion(s) stenosis through which a guidewire will not pass.

Page | 12

**CONFIDENTIAL AND PROPRIETARY:** This document and the information contained there-in may not be reproduced, used or disclosed without written permission from the Principal Investigators.

Version: 11\_dtd02Mar2023

IDE G210030

---

- 10) Last remaining vessel with compromised left ventricular function (defined as LVEF <30%)
- 11) Saphenous vein grafts
- 12) Angiographic evidence of thrombus
- 13) Angiographic evidence of significant dissection at the treatment site
- 14) Lesion(s) with previously placed stent within 10 mm (visual estimate)

## 6.4 Endpoints

The following are the planned study endpoints

### 6.4.1 PRIMARY ENDPOINT

- Post-procedural Minimum stent area (MSA in  $\text{mm}^2$ ), as assessed by final IVUS (post Stent and post-dilatation).

### 6.4.2 SECONDARY ENDPOINTS

- IVUS endpoints will be assessed at the following time points
  - Final IVUS (post Stent and post-dilatation)
    - In-segment Minimum lumen area ( $\text{mm}^2$ ), as assessed by IVUS after stent implantation and (optional) post-dilatation, referenced to the EEM
    - Minimum stent expansion (as defined as MSA  $\text{mm}^2$ ), as assessed by IVUS directly after stent implantation and post-dilatation
    - Mean stent expansion (%) –defined as mean stent area divided by the mean reference lumen area, where reference lumen area will be the average of the proximal and distal 10mm to the stent and/or the reference EEM at the site of MSA
    - Any dissection
    - Any malapposition
  - Pre-stent implantation post RA and CBA or POBA
    - Any dissection
    - Assessment of calcium fracture
- Angiographic endpoints measured in both in-stent, injured and in-segment (defined as injured or stent (whichever is larger) plus 5mm either end as feasible)

Page | 13

---

**CONFIDENTIAL AND PROPRIETARY:** This document and the information contained there-in may not be reproduced, used or disclosed without written permission from the Principal Investigators.

Version: 11\_dtd02Mar2023

IDE G210030

---

- Acute lumen gain (mm)
- Final residual diameter stenosis (%)
- Pre, pre-stent, and final minimum lumen diameter (mm)
- Pre-stent and final dissection type B or greater
- Final perforation (Ellis type  $\geq 2$ )
- Final side branch closure ( $\geq 1.5$ mm)
- Device-related endpoints as defined by any problems related to the devices, including but not limited to: balloon rupture, blade detachments, difficulty in withdrawing/advancing the device, or other device related problems as identified by the investigator.
- Clinical endpoints at 30-day and 270 day follow-up:
  - All-cause death (and further classified as cardiac and non-cardiac)
  - Myocardial infarction (as defined by the SCAI definition and Universal definitions, including peri-procedural myocardial infarction)
  - Target lesion revascularization
  - Target vessel revascularization
  - Stent thrombosis (definite/probable)
  - Major bleeding (BARC 3 or 5)
  - Vascular complications
  - Target Lesion Revascularization
  - Functional status (according to CCS class)

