## 6.5 Screening, Enrollment, and Randomization

All patients who are clinically suitable for treatment with a DES and who meet the study inclusion criteria while not meeting any study exclusion criteria will be approached for inclusion in the study. Subjects who agree to participate will sign an Institutional Review Board (IRB) approved study informed consent and will proceed to the cardiac catheterization lab for further assessment of the angiographic inclusion and exclusion criteria.

If the subject meets all inclusion criteria and does not meet any of the exclusion criteria, randomization will be performed before planned use of rotational atherectomy, but after the guidewire has successfully passed the lesion and the subject will be considered enrolled in the study. Randomization will be an integrated functionality of the EDC.

If the subject fails to meet inclusion/exclusion criteria, s/he will be considered a screening failure and will be excluded from data collection. Treatment of screening failures will then proceed as would occur within the standard of care outside of the study.

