## 7.3 Procedure overview

### 7.3.1 Study flow chart

### 7.3.2 Coronary Angiography

Coronary angiography for off-line QCA analysis will be performed 1) at baseline, 2) after each step of the lesion preparation, and 3) at the end of the procedure. After intracoronary injection of 100-200mcg of nitroglycerine, coronary angiography will be performed in two orthogonal projections aimed to minimize lesion foreshortening and differing at least 30° of rotation. The catheter tip, filled with dye, should be visible for QCA calibration and the lesion should ideally be located in the center of the field of view.

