### 9.2 Sample Size Rationale

The current study is investigating a novel approach for lesion preparation before stent implantation. As there is limited data available to estimate the expected MSA after rotational atherectomy + cutting balloon atherectomy strategy, no formal sample size calculation was performed. A sample size of 60 patients (total n=60) was chosen for this study. However, a sample size of 60 patients will be powered to detect effect sizes as listed below, given an estimated MSA of  $5.50\text{mm}^2 \pm 2.36\text{mm}^2$ , an equal variance, and a two-sided alpha of 0.05.

Table: Power Calculation

Sample Size	Effect Size (mean difference in MSA)	Power
60	1.6	0.733
60	1.7	0.783
60	1.8	0.828
60	1.9	0.866

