### **9.3.2 Secondary Endpoint Testing**

Time-to-event analyses using Kaplan Meier methods will be performed for dichotomous clinical secondary endpoint outcomes, event rates in both groups will be compared using the log-rank test.

A 2-sided independent samples Student's t-test will be used with a 2-sided alpha of 0.05 to test for differences in continuous secondary endpoints between the control and experimental groups.

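### Pre-procedure MLD belongs with the baseline characteristics and should serve as a covariate for the other MLD endpoints; the planned unadjusted t-tests are valid but can lose precision, most of all for acute lumen gain.

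*Combined protocol and SAP*

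**What the plan says.** Section 6.4.2 (Secondary Endpoints) includes, among the angiographic endpoints, "Acute lumen gain (mm)" and "Pre, pre-stent, and final minimum lumen diameter (mm)". It gives no formula for gain. It asks for angiographic endpoints in three regions: in-stent, injured and in-segment.

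Section 9.3.2 states: "A 2-sided independent samples Student's t-test will be used with a 2-sided alpha of 0.05 to test for differences in continuous secondary endpoints". No continuous endpoint is exempted, and sections 9.3 and 9.4 name no covariate. Section 10.4 refers to a pre-specified SAP, but the text supplied contains no adjusted analysis.

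On timing, section 7.3.2 says "Coronary angiography for off-line QCA analysis will be performed 1) at baseline, 2) after each step of the lesion preparation" and then again at the end of the procedure. Section 6.5 says "randomization will be performed before planned use of rotational atherectomy". Pre-procedure MLD is therefore planned for every patient and precedes any study treatment.

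Section 5 describes the secondary aim as the IVUS and QCA parameters after device use and at the end of the procedure. Pre-procedure MLD falls outside that description.

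**The concern.** Two things follow from reading 6.4.2 together with 9.3.2.

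- **A test with no treatment question behind it.** Pre-procedure MLD cannot respond to the assigned strategy. Under randomization its t-test rejects about 5% of the time whatever the treatments do.
- **Unused information.** Acute gain, read as final minus pre MLD, uses the baseline value with a slope fixed at 1. Pre-stent and final MLD do not use it at all. Neither choice is generally the most precise.

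Increased lumen gain is the first effect named in the study hypothesis (section 4.1), and the trial has only 60 patients. The gain and final-MLD tests can also give different answers from the same angiograms, with nothing in the plan to say which one counts. The stake is the precision and clarity of the angiographic comparison, not its validity.

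**Working it through.** **The plan's own figures.** The only power figures are for MSA (section 9.2): SD 2.36 mm², two-sided alpha 0.05, 60 patients, taken as 30 per arm under the 1:1 allocation. The noncentral t distribution with 58 df gives 0.733, 0.783, 0.828 and 0.866 for differences of 1.6 to 1.9 mm², exactly as stated. They have no bearing on MLD, for which the plan gives no figure.

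**Inputs.** From the documents: N = 60, 1:1, t-test at 0.05, baseline QCA required. Assumed, because the documents give neither: k = SD(pre MLD)/SD(final MLD) from 0.5 to 1.0, and r = correlation of pre with final MLD from 0 to 0.5. Gain is taken as final minus pre MLD.

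**Formulas**, with the variance of the arm difference relative to the final-MLD t-test:

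- final-MLD t-test: 1
- gain t-test: 1 + k² − 2kr
- ANCOVA: 1 − r² in large samples, multiplied by 1 + 1/56 = 1.018 at N = 60 for estimating the slope

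**Results.** The power columns use the standardised effect (0.736) that gives the final-MLD t-test 80.0% power. ANCOVA power includes the slope cost and uses 57 df.

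| k | r | gain | ANCOVA (large sample) | gain ÷ ANCOVA | power, gain t-test | power, ANCOVA |
|---|---|---|---|---|---|---|
| 0.5 | 0 | 1.250 | 1.000 | 1.25 | 70.7% | 79.3% |
| 0.5 | 0.3 | 0.950 | 0.910 | 1.04 | 82.0% | 82.9% |
| 0.5 | 0.5 | 0.750 | 0.750 | 1.00 | 89.9% | 89.4% |
| 0.75 | 0 | 1.5625 | 1.000 | 1.56 | 61.1% | 79.3% |
| 0.75 | 0.3 | 1.1125 | 0.910 | 1.22 | 75.7% | 82.9% |
| 0.75 | 0.5 | 0.8125 | 0.750 | 1.08 | 87.5% | 89.4% |
| 1.0 | 0 | 2.000 | 1.000 | 2.00 | 50.9% | 79.3% |
| 1.0 | 0.3 | 1.400 | 0.910 | 1.54 | 65.8% | 82.9% |
| 1.0 | 0.5 | 1.000 | 0.750 | 1.33 | 80.0% | 89.4% |

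Simulation of 4,000 trials at k = 0.75 and r = 0, 0.3 and 0.5 agreed with these powers to within two percentage points. In the same runs the t-test of pre-procedure MLD rejected in 4.5% to 5.0% of trials.

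**Final MLD.** The large-sample variance saving is r²: 0 at r = 0, 9% at r = 0.3, 25% at r = 0.5. Break-even after the slope cost is (1 − r²)(57/56) = 1, so r² = 1/57 and r ≈ 0.13. The same expression applies to pre-stent MLD, with r its own correlation with baseline.

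**Gain.** Since 1 + k² − 2kr = (1 − r²) + (k − r)², the gain t-test matches ANCOVA in large samples only when r = k. The final-MLD t-test matches it only when r = 0. Both cannot hold, because k is positive, so at least one of the two planned comparisons loses precision in large samples. At N = 60, ANCOVA has no net advantage for either comparison only if r is below about 0.13 and k is also below about 0.27 (2 × √(1/57) = 0.265).

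**The case against.** The strongest reply is that nothing here is wrong in the inferential sense. Unadjusted t-tests and change scores are valid under randomization, these are secondary endpoints of a pilot, and final MLD is already a planned comparison. That stands. At k = 0.7 and r = 0.2 the gain t-test has (1 + 0.49 − 0.28)/0.96 = 1.26 times the ANCOVA variance. A reader might infer that the trial in effect analyses only 60/1.26 ≈ 48 patients. That applies to the gain score alone: for final MLD at the same values ANCOVA saves 4% of the variance, about 2% after the slope cost.

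A reader might also infer that adjustment always narrows the interval. It does not. At r = 0 for final MLD, and at k = r = 0.5 for gain, ANCOVA is slightly worse once the slope is estimated.

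No sentence in the plan names a test of pre-procedure MLD. It follows from combining two sections, and section 9.4 separately provides for descriptive summaries by arm. Nor is it safe to say that an observed baseline difference could only be chance. Section 6.6 exits some patients after randomization, and the core labs are called independent without being described as blinded to arm. Neither point gives a reason to test the baseline value.

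Finally, no stented or injured region exists before treatment, so a covariate called simply pre MLD is undefined for those regions. This objection is correct and the fix has to settle it.

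**Conclusion.** The point holds as a labelling correction and a nearly free gain in efficiency. Pre-procedure MLD is a baseline value placed in an endpoint list whose continuous members are all to be t-tested.

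Over the assumed k and r, the gain t-test carries 1.00 to 2.00 times the large-sample variance of ANCOVA. For final MLD the saving is 0 to 25% before a slope cost of about 2%, and nil or slightly negative when r is below about 0.13. That at least one comparison loses precision in large samples follows from the algebra. The size does not: it rests on k, r and the reading of gain as final minus pre, none of which the documents supply.

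A reader might infer that the angiographic results would be biased or that the primary endpoint is affected. The documents support neither: the unadjusted tests remain valid, and the MSA analysis does not involve MLD. How CCS class should be analysed is a separate matter and adds no weight here.

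**What to change.** 1. In 6.4.2, move pre-procedure MLD out of the endpoint list. Report it by arm with the baseline characteristics, without a test.
2. In 6.4.2, define acute lumen gain as final MLD minus baseline lesion MLD, if that is the intended meaning.
3. In 9.3.2 or the SAP, before unblinding, replace the t-test for final MLD and acute gain by one linear model for final MLD. Its terms are arm and baseline lesion MLD, meaning the pre-treatment MLD of the target lesion, used as the covariate for every measured region. Report the adjusted arm difference with its 95% CI. When gain subtracts that same baseline value, the model gives the same adjusted arm difference for gain, so one analysis serves both.
4. Apply the same model to pre-stent MLD.

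The cost is a few sentences and one residual degree of freedom (58 to 57), about 2% of variance if the baseline value proves uninformative. No new data or patients are needed. Naming the covariate in advance also prevents a later choice between adjusted and unadjusted results.

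### Perforation and side-branch closure are read only at the final angiogram, so events from lesion preparation that resolve earlier are missing from the core-lab counts by arm

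*Combined protocol and SAP*

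**What the plan says.** Section 5 includes among the secondary endpoints "procedure related complications, and 1 & 9 - month MACE among the list". It does not define the complications.

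The angiographic list in section 6.4.2 attaches time points to its items. Minimum lumen diameter is read at three: before treatment, before stenting and at the end. Dissection is read at two: "Pre-stent and final dissection type B or greater". The other two complications carry one time point each: "Final perforation (Ellis type" 2 or more) and "Final side branch closure" for branches of at least 1.5 mm.

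Section 7.3.2 already requires angiograms at baseline, "after each step of the lesion preparation, and 3) at the end of the procedure". Section 13.1 has the core lab evaluate all the procedure angiograms that sites submit.

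**The concern.** The arms differ in lesion preparation: cutting balloon or plain balloon after rotational atherectomy. All patients then receive a stent (section 6.1). Stenting, any post-dilatation and any repair therefore fall between the randomized step and the only reading of these two complications.

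This has two consequences. A perforation that is sealed, or a branch that reopens, before the last angiogram is recorded as no event. A branch closed by the stent is recorded in the same way as one closed by preparation, so the endpoint mixes causes. Section 11.2 lists both perforation and side-branch occlusion among the risks of the cutting balloon, so a pilot of this strategy should be able to state how often each occurred in each arm.

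**Working it through.** **1. Time points in section 6.4.2, side by side**

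| Item | Before stenting | Final |
|---|---|---|
| Minimum lumen diameter | yes (and before treatment) | yes |
| Angiographic dissection, type B or greater | yes | yes |
| IVUS dissection | yes | yes |
| IVUS calcium fracture | yes | not listed |
| Perforation, Ellis type 2 or more | not listed | yes |
| Side-branch closure, 1.5 mm or more | not listed | yes |

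The IVUS rows rest on the heading "Pre-stent implantation post RA and CBA or POBA" and on the final-IVUS list. The IVUS part of 6.4.2 places the final run after stenting and post-dilatation. Final is thus a time point in this section, not a loose word for overall, and a core lab following the text would score end-of-procedure status.

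**2. What else captures these events**

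- Device problems have no time limit: "Device-related endpoints as defined by any problems related to the devices, including but not limited to: balloon rupture, blade detachments". They are identified by the investigator and concern the device, not a core-lab finding in the vessel.
- The infarction endpoint counts events "including peri-procedural myocardial infarction". It would register a perforation or closure only through its consequence.
- Adverse events are collected from randomization and include procedural events (sections 12 and 12.1). Sites report them, and the investigator makes the first judgement of relatedness (sections 12.2 and 12.3).
- The events committee adjudicates only serious events that are eligible as endpoints (section 12.6). With the endpoint fixed at final, it is unclear whether a resolved perforation qualifies.
- The stopping rule in section 11.8 counts only flow-limiting dissections with periprocedural infarction.

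None of these gives a core-lab count by arm of perforation or side-branch closure during preparation.

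**3. Possible size**

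The plan states no figure for either complication. Its only power figures, for minimum stent area, reproduce (two-sample t-test, 30 per arm, SD 2.36: 0.733, 0.783, 0.828, 0.866) but have no bearing here.

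For illustration, let *p* be the rate of one such complication at any time in the procedure and *q* the share resolved before the final angiogram. Both are assumptions. With 60 patients:

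- expected events = 60*p*
- expected events counted = 60*p*(1 − *q*)
- probability of counting at least one = 1 − [1 − *p*(1 − *q*)]^60

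| *p* | *q* | Expected events | Counted at final | P(at least one), any time | P(at least one), final only |
|---|---|---|---|---|---|
| 2% | 50% | 1.2 | 0.6 | 0.70 | 0.45 |
| 2% | 90% | 1.2 | 0.12 | 0.70 | 0.11 |
| 5% | 50% | 3.0 | 1.5 | 0.95 | 0.78 |
| 5% | 90% | 3.0 | 0.3 | 0.95 | 0.26 |

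Over wider ranges (*p* 1–10%, *q* 25–90%), 0.06 to 4.5 events are counted against 0.6 to 6.0 occurring, so 10% to 75% of them.

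**4. Could complete counting show a difference between arms?**

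If all of *k* events fall in one arm of 30, two-sided Fisher p = 2·C(30, *k*)/C(60, *k*):

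- *k* = 2: 2 × 435/1,770 = 0.49
- *k* = 3: 2 × 4,060/34,220 = 0.24
- *k* = 5: 2 × 142,506/5,461,512 = 0.052

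At 1 to 3 events in total, no split between arms is significant under either definition.

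**The case against.** The strongest reply is that the gap is narrow and partly closed by other means. A perforation that needed sealing would plausibly meet the serious-event definition in section 12.1, which covers intervention to prevent life-threatening injury. Serious events are reported within 48 hours (section 12.3) and fully source-verified (section 13.5.2), and the medical monitor reviews all adverse events (section 12.5). Section 9.4 provides frequencies by allocation. This stands as far as it goes: such events need not vanish from the record. But they would be site-reported, and an event treated without meeting the serious criteria would be an ordinary adverse event with no independent reading.

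A second reply is that closure persisting at the end of the procedure is a legitimate outcome in its own right. That is fair, and it is a reason to keep the final status as a separate line.

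A third is that adding a pre-stent reading does not by itself produce an any-time endpoint, because an event that arises and resolves during stenting or post-dilatation would still be missed. That is correct, and the fix has to allow for it.

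Three stronger inferences are tempting and should not be drawn:

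- That preparation complications in general go uncounted. Dissection is read before stenting on both IVUS and angiography, and device problems are open-ended in time.
- That the section 5 objective is left unanswered. It is answered in part by dissection, device problems, peri-procedural infarction, bleeding and vascular complications.
- That a finding of no difference would be an artefact of timing. With so few events it would be expected from the sample size alone, and nothing in the documents suggests that resolved events would fall mainly in one arm. Section 9.3.2 also names no test for binary angiographic endpoints, so these two items are in effect descriptive.

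**Conclusion.** The point holds in limited form. As written, perforation and side-branch closure miss events that arise in lesion preparation and resolve before the last angiogram, and they do not separate preparation from stenting as the cause. The section 5 objective is therefore answered incompletely for these two harms.

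The loss is in complete descriptive counts by arm. Its size is unknown, because the documents give neither event rates nor the share resolved; the table above rests wholly on assumed values. The reading of the time points rests on the text alone and is firm. If the sponsor meant occurrence at any time, the wording still needs correcting. The primary endpoint and the sample size are unaffected.

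**What to change.** In section 6.4.2, give both items the time points already used for dissection, pre-stent and final, with the core lab reading them from the angiograms that section 7.3.2 requires after each preparation step. Then report, by arm:

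- (a) any occurrence during the index procedure, combining the core-lab pre-stent and final readings with site-reported procedural events, so that events arising and resolving during stenting or post-dilatation are included;
- (b) status unresolved at the end of the procedure, as a separate line.

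The cost is protocol and SAP wording and a few extra core-lab and CRF fields. No further imaging or patients are needed. The reported complication rates may look less favourable than under final-only scoring.
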